## 6 STATISTICAL ANALYSIS PLAN

### 6.1 Statistic analysis

A descriptive analysis of the variables included in the study will be carried out. Descriptive statistics will be calculated, including frequencies and percentages for categorical variables and means  $\pm$  standard deviations or medians with interquartile ranges for continuous variables. Univariate analysis is planned to identify variables related to developing complications, using Chi-square tests. To identify risk factors related to mortality, univariate logistic regression models will be constructed. For survival analysis, Kaplan-Meier curves will be plotted, and log-rank tests are going to be used to evaluate differences between the curves. A column graph graft creation is planned to show the tumor response. In all cases where possible, the 95% confidence interval significant at  $p<0.05$  will be calculated. All effects are considered. All statistical analysis will be performed with the SAS 9.4 (SAS Institute Inc., Cary, NC, USA).

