## 3 STUDY POPULATION

### 3.1 Target population

Patients with confirmed HCC and stage B according to the BCLC classification. Patients with a less advanced stage (BCLC stages 0 and A) but who are not candidates or expressly reject radical treatments with surgery or radiofrequency.

Three possible groups of patients are considered:

- A.- Patients unfit for surgery or liver transplantation due to tumor extension, age and / or comorbidities.
- B.- Patients not eligible for a liver transplant for exceeding the Milan criteria but with the possibility of experiencing a backward step to a previous stage (down stage) by TACE within these criteria
- C.- Patients eligible for a liver transplant on the waiting list: to prevent tumor progression while on the waiting list.

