#### **4.2 Follow-up**

After the first TACE procedure, the following evaluations will be carried out:

1. Clinical and analytical control 10-20 days after discharge according to usual practice: Clinical visit in which the general condition of the patient is assessed and will be asked whether or not he had Sd. Post-pay, its duration and intensity. Analytical including blood count, coagulation tests, basic biochemistry, transaminases and bilirubin. The study may be extended with more complete imaging or analytical tests if the physician considers it necessary.
2. Dynamic liver CT or MRI every 3 m for the first 6 months and then twice a year according to usual practice.
3. Clinical and laboratory review every 3 m the first 6 months and then twice a year as usual practice until the progression, death or loss of patient follow-up, with a maximum of 5 years.
  - a. Quality of life assessment (ECOG)
  - b. Laboratory assessment
  - c. Evaluation of safety and efficacy and assessment of retreatment if appropriate.

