### **5 TUMOR RESPONSE ASSESSMENT**

#### **5.1 Study Variables**

Related to the patient and the disease: age, gender, etiology of liver disease, diagnosis of HCC, previous nodules treated with surgery, ablation or TACE, Child-Pugh score, BCLC stage of the tumor, size, location and number of patients. nodules, segmental vascular

invasion of the portal vein, bilioenteric shunt or previous biliary prosthesis, carrier of porto-systemic shunt, relevant concomitant pathologies.

- Variables related to the primary objective:

**Post-embolization syndrome:** in an adverse effect of TACE that is defined as a picture of abdominal pain, fever  $<38.5^{\circ}\text{C}$ , and variable degree leukocytosis that appears 24 hours after the procedure and can last up to 10 days. It can be accompanied by nausea, vomiting and asthenia. It is related to tissue necrosis and is self-limited, its treatment is symptomatic. Its incidence is variable and linked to the volume of necrotic tissue.

**Early adverse events** derived from the procedure during the first 30 days:

1. Liver failure defined by ascitic decompensation with elevation of serum Br, jaundice and transaminases  $>x5$  and / or hepatic encephalopathy.
2. UGIB of peptic or varicose origin
3. Intense pain that requires continued iv medication
4. High fever that is not justified by Sd. post refund
5. Liver abscess
6. Coagulative portal thrombosis
7. Acute pancreatitis
8. Acute cholecystitis
9. Renal failure, elevation of serum Cr  $\times 2$  its baseline value.
10. Pleural effusion

**Late adverse events** arising from the procedure between the first 30 days and 6 months:

1. Intrahepatic bile duct injury defined by dilation of biliary radicals with cholestatic symptoms.

Additional therapies against cancer (sorafenib, radioembolisation, symptomatic treatment) will be documented for all patients every three months until death.

**Mortality** in the first 30 days after treatment

- Variables related to secondary objectives: the information will be obtained from imaging studies performed interchangeably with liver MR or CT using intravenous contrast and performing three-phase dynamic studies (arterial, portal and balance phase). Imaging studies will be evaluated according to RECIST 1.1 criteria.

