### 7.2 Detection and documentation

It is the responsibility of the investigator to document all adverse events that occur during the study. At each visit / evaluation, all adverse events observed by both the researcher, and one of his clinical collaborators, such as those reported by the subject spontaneously or in response to a direct question, will be evaluated by the investigator and noted in the section on Adverse events in the subject's data collection notebook.

Adverse events must be recorded at each evaluation visit throughout the study. The nature of each event, the start time after the procedure under evaluation, the duration, severity and relationship with it should be established. The details of any corrective treatment must be recorded on the corresponding pages of the data collection notebook. The initial symptomatology must be well documented at the selection visit. It is important to correctly collect the baseline information in order to interpret the data of subsequent visits.

Follow-up of adverse events: Investigators should monitor subjects with adverse events until they have decreased, disappeared or until the process has stabilized. Reports regarding the course of the evolution of the subject should be sent to the clinical trial monitor.

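### Late bile-duct injury (day 30 to month 6) is planned as a plain percentage with no denominator or incomplete-follow-up rule, so with an all-treated denominator, review ended by progression or loss would understate the 6-month risk

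*Combined protocol and SAP*

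**What the plan says.** Section 5.1 (Study Variables) has one late adverse event under the primary-objective variables: "Intrahepatic bile duct injury defined by dilation of biliary radicals with cholestatic symptoms". Its window is given as "arising from the procedure between the first 30 days and 6 months". The definition needs an imaging finding and a clinical one.

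Section 6.1 (Statistic analysis) plans descriptive statistics, "including frequencies and percentages for categorical variables". Complications are also to be examined for related factors: "Univariate analysis is planned to identify variables related to developing complications, using Chi-square tests". Time-to-event methods appear only for survival: "For survival analysis, Kaplan-Meier curves will be plotted". No denominator, censoring rule or competing-event rule is given for late events.

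Section 4.2 (Follow-up), item 3, runs the clinical and laboratory review, which includes the safety evaluation, "until the progression, death or loss of patient follow-up, with a maximum of 5 years". Section 7.2 says: "Adverse events must be recorded at each evaluation visit throughout the study".

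Section 3.1 (Target population) admits transplant candidates: "Patients eligible for a liver transplant on the waiting list: to prevent tumor progression while on the waiting list". The secondary objectives say how transplant affects tumor control. Nothing says how it affects late adverse events.

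**The concern.** The Background names damage to the bile radicals as the potential harm of very small particles, so this variable carries a central safety question of the study. It can be fully observed only in a patient reviewed to month 6. If review ends at progression found on the month-3 scan, about 60% of the window is unseen, and even if imaging continues, the symptom half of the definition depends on a review that has ended.

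A bare percentage must do something with such patients. Kept in the denominator, they count as injury-free and the figure leans in the product's favour. Dropped, the remaining patients are a selected group. The plan does not choose, so the choice could be made after the data are seen. The same binary variable would feed the Chi-square tests. The confidence interval reflects sampling error only and would not show this shift.

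**Working it through.** **The plan's own figure.** Section 6.2 assumes 130 patients and an event proportion of 1%. Half-width = 1.96 × √(0.01 × 0.99 / 130) = 1.71 percentage points, as stated. Solving back for 1.71 points gives n = 130.06. The formula treats all 130 patients as fully observed.

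**Assumptions.** The documents give no bile-duct injury rate and no early-exit rate. I take a 5% net risk over the window (the risk if nobody left) and exits of 10% to 40%, with injury at a constant hazard. On a window of length 1, λ = −ln(0.95) = 0.051293.

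**All exits treated as censoring, all treated patients as denominator.** With exit fraction q at a constant hazard, μ = −ln(1 − q) and

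crude = λ/(λ + μ) × [1 − exp(−(λ + μ))].

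For q = 20%: μ = 0.223144, and 0.051293/0.274437 × (1 − 0.95 × 0.80) = 0.1869 × 0.24 = 4.49%.

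Two other exit patterns use crude = (1 − F) × 0.05 + F × r, where F is the fraction leaving and r is the injury risk of a leaver before leaving:

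- Exits uniform over the window: r = 1 − 0.05/0.051293 = 0.0252.
- Exits all at the month-3 scan: (91 − 30)/153 = 0.40 of the window has been seen, so r = 1 − 0.95^0.40 = 0.0202.

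| Exits | Constant exit hazard | Uniform | All at month 3 |
|---|---|---|---|
| 10% | 4.75% | 4.75% | 4.70% |
| 20% | 4.49% | 4.50% | 4.40% |
| 30% | 4.21% | 4.26% | 4.11% |
| 40% | 3.92% | 4.01% | 3.81% |

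The relative shortfall from 5% is about 5% to 22% for exits spread over the window and 6% to 24% for exits at month 3. Under the constant exit hazard the ratio is almost the same at true risks of 1%, 2% and 10%.

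**Exits split by type.** Death and transplant are competing events (hazard μc); progression and loss are censoring (hazard μl). The crude share uses λ + μc + μl. The right comparator is now the cumulative incidence, which uses λ + μc only.

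| Death/transplant | Progression/loss | Crude | Cumulative incidence | Ratio |
|---|---|---|---|---|
| 10% | 10% | 4.51% | 4.75% | 0.95 |
| 10% | 20% | 4.27% | 4.75% | 0.90 |
| 20% | 0% | 4.49% | 4.49% | 1.00 |

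The last row shows that death and transplant alone produce no understatement. Censoring them in 1 minus Kaplan-Meier would instead give 5.00% against 4.49%, an overstatement.

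**Completers as denominator.** If exit is unrelated to injury and every leaver is dropped, the completers' rate stays at 5%. If injured leavers are kept and only uninjured leavers dropped, 20% exits give 0.0449/(0.95 × 0.80 + 0.0449) = 5.6%. If leavers carry a higher injury risk and all are dropped, the figure falls below the true risk. No single direction follows.

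**Against sampling error.** At 1% with 20% exits all censored, 1.17 cases are expected instead of 1.30 among 130. At 5% it is 5.83 instead of 6.50. The Wald half-width at 5% is 1.96 × √(0.05 × 0.95/130) = 3.7 points. The shortfalls in the first table run from 0.25 to 1.2 points.

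**The case against.** The strongest reply is that an early stop in safety review is not established. In section 4.2, item 3, the clause about progression follows the twice-yearly phase and can be read as applying only after month 6. Item 2 schedules CT or MRI every 3 months to month 6 with no stop at progression. The Summary gives fixed visits, including months 3 and 6, and 2 years of follow-up after final treatment. Section 5.1 documents further cancer therapies every three months until death, and section 7.2 requires recording throughout the study. This stands as a contradiction to be reconciled. It does not settle the matter, because under either reading loss to follow-up has no rule.

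A reader might infer that the plan itself counts leavers as injury-free. It does not say so: the all-treated denominator is a likely default, not written text. A reader might also infer that early deaths and transplants bias the percentage downward. They do not, as the split calculation shows.

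On size, the reply is fair. The study is descriptive, the bias lies inside the sampling error, entry requires a life expectancy above six months, and nothing in the documents supports exits of 30% to 40% within five months. The bullets under Primary Objective do not name this late event, although section 5.1 places it among the primary-objective variables.

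**Conclusion.** The point holds in a limited form. The plan summarises late bile-duct injury only as a percentage and does not say who is in the denominator or how incomplete follow-up is handled. With all treated patients as denominator, review ended before month 6 by progression or loss makes the figure too low. Death and transplant do not contribute. With month-6 completers the direction is open.

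For an assumed 5% risk, the crude figure would be about 4.75% with 10% exits, 4.5% with 20% and 3.9-4.0% with 40% spread over the window, if every exit is censoring; it is lower if exits cluster at month 3. The gap is smaller when exits are mixed: 4.51% against 4.75% with 10% competing and 10% censored. These sizes rest on assumed risks and exit fractions and on exit being unrelated to injury. A claim of serious understatement is not supported. A systematic shift in a safety variable that the interval does not reflect, and that is cheap to remove, still justifies changing the method.

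**What to change.** - In section 6.1, report late bile-duct injury as a 6-month cumulative incidence (Aalen-Johansen) with a 95% interval. Treat death and liver transplant as competing events and censor at the last safety review.
- State the time origin. Section 4.2 starts follow-up after the first TACE and allows for retreatment, while the Summary counts follow-up from the final treatment.
- Beside it, give the crude count with its denominator and the numbers still under review at months 3 and 6.
- Reconcile section 4.2 with the Summary and sections 5.1 and 7.2 on whether late adverse events are recorded after progression. If they are recorded to month 6 for everyone, progression is no longer a reason for censoring.
- If review does stop at progression, add a sensitivity analysis. Aalen-Johansen assumes uninformative censoring, and patients who progress may differ in injury risk. One option is to let the injury hazard after progression be a stated multiple of the hazard before it and show the result over a range.

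The cost is SAP wording, a little more analysis work, and the need for event, death, last-review and transplant dates. Any change to how long late events are recorded would also need protocol text.

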## 2 STUDY DESIGN

The study has been conceived as a multicenter, international, observational, post-authorization, prospective follow-up study (EPA-SP). It is planned to include between 100 and 150 patients with non-removable HCC treated with the 100  $\mu$ m Embozene TANDEM™ microspheres (drug-releasing microparticles with doxorubicin loading) for enhanced cytotoxic transarterial embolization therapy with hepatocellular carcinoma microparticles.

10 University Hospitals of Spain with recognized experience in treatments with TACE will participate. Each center must recruit a minimum of 5 patients.

All the associated researchers are certified in Vascular and Interventional Radiology with recognized experience in liver cancer intervention, in the administration of small embolic microspheres, in the management of microcatheters and in ultraselective catheterization.

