### 6.2 Sample Size Calculation

It is an observational and descriptive study. As far as we know, no data have been published in the literature on the proportion of adverse effects / complications associated with the administration of QETA with 100 micron microspheres, so it has not been possible to make a sample size predetermination based on data previous. It is intended to include 10 patients per center, which would make a total of 130 patients. With this sample size, an accuracy of 1.71% can be achieved in the estimation of a proportion through a bilateral asymptotic confidence interval of 95.00%, assuming that the proportion of the event is 1.00%.

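### Chi-square is the only test named for complication risk factors; for individual complications as rare as about 1–2% its uncorrected form is unreliable, and section 6.1 has no exact-test or minimum-event rule

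*Combined protocol and SAP*

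**What the plan says.** Section 6.1 (Statistic analysis) sets out the search for factors associated with complications in one sentence: "Univariate analysis is planned to identify variables related to developing complications, using Chi-square tests". The same section refers to "the 95% confidence interval significant at" p<0.05. It names no exact test, continuity correction, minimum expected count or minimum number of events. Logistic regression is planned only for mortality.

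Section 6.2 (Sample Size Calculation; same text in 3.4) reports that no published complication rate was available. It gives a precision figure instead: "an accuracy of 1.71% can be achieved in the estimation of a proportion", from a "bilateral asymptotic confidence interval of 95.00" per cent, "assuming that the proportion of the event is 1.00" per cent, with a recruitment aim "which would make a total of 130 patients". Section 2 gives a range: "It is planned to include between 100 and 150 patients".

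Section 5.1 lists ten early adverse events and one late one, several of them specific (liver abscess, acute pancreatitis, acute cholecystitis, bile duct injury). Among the baseline variables it lists segmental portal invasion and "bilioenteric shunt or previous biliary prosthesis, carrier of porto-systemic shunt, relevant concomitant pathologies". No frequencies are given, and 6.1 defines neither the complication outcome nor the candidate factors.

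**The concern.** The chi-square p-value relies on a large-sample approximation, usually trusted when every expected cell count is at least about 5. If the outcome is a single complication of the order of 1%, only one or two events are expected in the whole study, and no two-group split comes near that.

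The p-value then depends mainly on how many patients happen to be in the category where the event falls. One chance event in a small category looks like a strong association, whereas in balanced groups the test almost never rejects. A device safety report could name a risk factor on the strength of one patient.

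**Working it through.** **Inputs.** N = 130 and an event proportion of 1.00% (6.2); threshold 0.05 (6.1). Category sizes are not in the documents, so a range of m = 5 to 65 patients out of 130 is assumed. The chi-square is taken as the uncorrected Pearson statistic, also an assumption, because 6.1 does not say.

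**The plan's own figure.** 1.96 × √(0.01 × 0.99 / 130) = 1.71%. This reproduces the stated precision.

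**Expected events.** 130 × 0.01 = 1.3, or 0.65 per group in a 65:65 split. From Binomial(130, 0.01): P(0) = 27%, P(1) = 36%, P(2) = 23%. With 100 patients, the lower end of the range in section 2, 1.0 event is expected.

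**One event, falling in a category of m patients.** The Pearson statistic reduces to N(N − m) / [m(N − 1)], to be compared with 3.84. Fisher's p-value is m/N for m below 65, which is the chance that a single event lands in that category when there is no association.

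| m | Pearson statistic | Chi-square p | Fisher p |
|---|---|---|---|
| 13 | 130×117/(13×129) = 9.07 | 0.0026 | 0.10 |
| 26 | 130×104/(26×129) = 4.03 | 0.045 | 0.20 |
| 27 | 130×103/(27×129) = 3.844 | 0.0499 | 0.21 |
| 28 | 130×102/(28×129) = 3.67 | 0.055 | 0.22 |

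The single-event threshold is therefore m = 27 (27/130 = 21% of the sample) for the uncorrected test, m = 7 with the Yates correction and m = 6 for Fisher. With two events, one of them in the category, it is m = 12 for the uncorrected test and m = 3 for Fisher.

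**Type I error of the nominal 5% test.** Two binomials with equal rates were enumerated in full and the probabilities of all tables with p<0.05 summed.

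| Split | Chi-square, 1% rate | Fisher, 1% rate | Chi-square, 5% rate | Chi-square, 10% rate |
|---|---|---|---|---|
| 5:125 | 4.7% | 1.5% | 4.8% | 5.5% |
| 10:120 | 6.5% | 0.4% | 4.9% | 4.2% |
| 13:117 | 4.3% | 0.7% | 4.0% | 4.3% |
| 20:110 | 6.7% | 0.6% | 4.0% | 4.0% |
| 26:104 | 9.2% | 1.1% | 3.9% | 4.6% |

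For 65:65 at a 1% rate, chi-square gives 0.4%. Given at least one event, the 26:104 figure at 1% rises to 12.6%. At a 2% rate, 26:104 still gives 7.9%. Over the splits examined, from 5:125 to 65:65, the range at 5–10% rates is 3.9–5.5%.

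**Can any test find a risk factor at 1%?** In a 65:65 split Fisher needs 6 versus 0 (5 versus 0 gives p = 0.058). The chance of 6 or more events in 130 patients is 0.2%. The chance of 5 or more is 1 − (0.2708 + 0.3555 + 0.2316 + 0.0998 + 0.0320) = 1.0%.

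**The case against.** The strongest reply is that the 1.00% is not a forecast of complications. Section 6.2 says no prior data exist and uses 1% for an unnamed event to illustrate precision. A reader might infer that the plan expects about 1.3 complications in total and will therefore report chance findings as risk factors. The documents do not support that. Complications in 6.1 are undefined, and a pooled outcome that includes post-embolization syndrome, pain, fever and pleural effusion could be far more frequent. At 5–10% the test is close to nominal. This stands, and it confines the point to rare individual complications, which 6.1 does not exclude.

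Four further limits also stand:

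- Even at 1% the inflation is irregular. The 13:117 split that gives the striking p = 0.0026 has an overall type I error of 4.3%, below nominal, and that particular table has a probability of only about 3.6% (0.356 × 0.10).
- The 27-patient threshold requires the uncorrected statistic.
- That shunts, prostheses or segmental invasion will form small categories is plausible, but no figure in the documents shows it. Treating the 5.1 baseline list as the set of factors to be tested is also an inference.
- The study describes itself as observational and descriptive, and no decision rule depends on this screen.

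Nor is Fisher's test a complete answer. It still gives p<0.05 for one event in 6 or fewer patients. Where chi-square is already adequate it is conservative: 1.8% against 3.9% at a 5% rate with a 26:104 split.

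**Conclusion.** The point holds for rare individual complications, of the order of 1–2%, analysed with the uncorrected chi-square test. There, one event in a category of up to 27 of 130 patients is nominally significant, and at a 1% rate the actual size of the 5% test runs from 0.4% to 9.2% according to the split. It does not hold for a common pooled complication outcome, and with a continuity correction the single-event effect reaches only categories of 7 or fewer. The category sizes and the choice of statistic are assumptions that the documents leave open. Severity is minor: the primary safety objective is met by description, and those estimates are untouched.

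**What to change.** Amend the sentence in 6.1 as follows:

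1. Complications with fewer than 5 events are listed case by case and not tested. This is the key part, because it removes the single-event finding that Fisher's test alone would leave in very small categories.
2. For the other outcomes, use Fisher's exact or an exact mid-p test when any expected count is below 5, and chi-square otherwise. Mid-p limits the conservatism.
3. Label the screen exploratory.
4. State that risk factors for a complication as rare as 1% cannot be identified with 130 patients.

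Naming the complication outcome or outcomes to be screened would also settle how far the problem reaches. Odds ratios with Firth penalised-likelihood intervals are an optional addition. The cost is a change of SAP wording, with no new data or patients, and some conservatism in sparse tables.

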**SUMMARY**

Object of the investigation	Embozene TANDEM™ 100 µm microspheres
Full Title	Multicenter spanish observational, prospective study to evaluate the safety of transarterial Chemoembolisation (TACE) with tight calibrated and doxorubicin-releasing microspheres of 100 microns in the treatment of Hepatocellular Carcinoma (HCC)
Study Identifier	FJD-TAN-2014-01. Version 1.1, March 15 th , 2015
Study Description	Prospective Post-authorization study of follow-up (EPA-SP)
Promotor	[name], MD, PhD Vascular and Interventional Radiology Service Ramon y Cajal University Hospital. [name]. [contact] [contact]
Principal Investigator	[name], MD, PhD Vascular and Interventional Radiology Service Ramon y Cajal University Hospital. [name]. [contact] [contact]
Primary Objective	Safety and tolerability of DEB-TACE of non-resectable HCC, using 100-µm doxorubicin-loaded microspheres
Secondary Objectives	6-, 12- and 24-month local tumor response and 2-year Over All Survival
Number of Investigators	10 Spanish University Hospitals (See annexed II)
Number of participants	130
Inclusion Criteria	Confirmed diagnosis of HCC, Subject is competent and willing to provide written informed consent, Adults (male or female) patients ≥ 18 years of age, ECOG performance status is 0 – 1 or Child-Pugh classification is A, B7, Multinodular or single nodular tumor ≥3 – 9 cm, No invasion in the major blood vessels, Proper blood, liver, renal, heart function: testing result within 2 weeks of start, No current infections requiring antibiotic therapy, Not actively on anticoagulation drugs, Measureable disease per the modified Response Evaluation Criteria in Solid Tumors (mRECIST), Life expectancy ≥ 6 months
Exclusion Criteria	(ECOG performance status ≥2; or Child-Pugh class B8 or C, Bilirubin levels >3 mg/dl, HCC with large vessel or biliary duct invasion, diffuse HCC or extrahepatic spread, Patients in which any of the following are contraindicated or present (The use of doxorubicin, MRI or CT scans, Hepatic embolization procedures, WBC < 3000 cells/mm  , neutrophil < 1500 cells/mm  , Cardiac ejection fraction < 50 percent, Elevated creatinine greater than or equal to 2.5 mg/dl, Impaired

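### Chi-square is the only association test named for complications, so age and tumour size must be grouped at cut-points that the plan does not fix; continuous logistic terms would avoid this at no cost

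*Combined protocol and SAP*

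**What the plan says.** Section 6.1 commits to a univariate search for predictors of complications and then turns to mortality: "using Chi-square tests. To identify risk factors related to mortality, univariate logistic regression models will be constructed". No other association method is named for complications; regression is given only to the second outcome, mortality.

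Section 5.1 lists the patient and disease variables. They include age and, with a slip in the text where the number of nodules is evidently meant, "Child-Pugh score, BCLC stage of the tumor, size, location and number of patients. nodules". Section 6.1 recognises that some variables are continuous, but only when summarising them, by means with standard deviations or "medians with interquartile ranges for continuous variables". Neither section gives cut-points or a number of groups for testing.

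The only size range is in the Summary: "Multinodular or single nodular tumor ≥3 – 9 cm". Child-Pugh is limited to class A or B7 in the Summary and to B7 or better in section 3.2, so the score takes the values 5, 6 and 7. On post-embolization syndrome, section 5.1 says: "Its incidence is variable and linked to the volume of necrotic tissue".

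**The concern.** A chi-square test works on a table of categories. Age and tumour size are continuous, so they can enter only after being cut, and with no cut-points in the plan the thresholds would be chosen with the data in hand. The result then depends on that choice, and information is lost within each group. Child-Pugh points and nodule count can be tabulated at their own levels without cutting, but an unordered test spends extra degrees of freedom and disregards the ordering.

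The plan already uses logistic regression for mortality, so a method that avoids these losses is at hand. Section 6.1 also wants 95% confidence intervals wherever possible, whereas a chi-square test by itself yields only a p-value. At stake is a lower chance of finding a real gradient in risk, and a finding that is harder to defend if a cut-point was picked after the fact.

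**Working it through.** **Inputs from the documents.** N = 130, assumed event proportion 1.00% and stated precision 1.71% (sections 3.4 and 6.2); significance level 0.05 (section 6.1), taken as two-sided; tumour size 3 to 9 cm (Summary).

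**Assumptions, because the documents give no figures.** Complication rates of 10% and 30%; odds ratios of 1.7 and 2.0 per SD; log-odds linear in the predictor; the shape of the predictor's distribution.

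**1. The plan's own figure.** 1.96 × √(0.01 × 0.99 / 130) = 0.0171, or 1.71%. It reproduces. At that rate the expected number of events is 130 × 0.01 = 1.3, too few for any risk-factor test.

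**2. Information kept after grouping.** For small effects, the efficiency of a grouped predictor relative to a linear term is the between-group variance of X divided by its total variance.

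- Normal predictor, median split: the group means are ±√(2/π) SD, so efficiency = 2/π = 0.637. The loss is 36%, and 130 × 0.637 ≈ 83 effective patients.
- Uniform over 3 to 9 cm, median split: total variance 6²/12 = 3; group means 4.5 and 7.5 around 6, so between-group variance 1.5² = 2.25; efficiency 2.25/3 = 0.75, loss 25%.
- Uniform, k equal groups: efficiency 1 − 1/k², so tertiles lose 11% and quartiles 6%.

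Loss by distribution and split (normal median from the formula above, the rest computed numerically):

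| Predictor | Median | Tertiles | Quartiles | 70/30 | 80/20 |
|---|---|---|---|---|---|
| Normal | 36% | 21% | 14% | 42% | 51% |
| Uniform, 3–9 cm | 25% | 11% | 6% | 37% | 52% |
| Lognormal, log-SD 0.5 | 48% | 33% | 25% | 39% | 39% |
| Exponential | 52% | 35% | 27% | 38% | 35% |

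The range is about 6% to 52%; a lognormal with log-SD 0.8 and a median split reaches 63%. These figures leave out the further cost of the 2 or 3 degrees of freedom of an unordered test on tertiles or quartiles.

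**3. Power at N = 130** (20,000 simulated cohorts per row; logistic score test on the continuous term against Pearson chi-square on the groups):

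| Predictor | Event rate | OR per SD | Continuous | Median | Tertiles | Quartiles |
|---|---|---|---|---|---|---|
| Normal | 30% | 1.7 | 76% | 57% | 55% | 52% |
| Normal | 10% | 1.7 | 42% | 28% | 25% | 22% |
| Normal | 10% | 2.0 | 62% | 42% | 40% | 35% |
| Uniform | 30% | 1.7 | 77% | 64% | 61% | 57% |

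A separate simulation gave 75% against 56% (30%, OR 1.7) and 43% against 29% (10%, OR 1.7), so the figures are stable to about one point. With no effect, rejection rates at these event rates were 4.8–5.2% for the continuous test and 4.1–5.5% for the grouped tests, so the gap is not bought with a higher false-positive rate.

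**4. Check by hand.** The approximate non-centrality is N·p(1 − p)·(ln OR)²·efficiency. At 30% and OR 1.7: 130 × 0.21 × 0.2816 = 7.69, whose root is 2.77, so power ≈ Φ(2.77 − 1.96) = 79%. Multiplied by 0.637 it is 4.89, root 2.21, power ≈ 60%. The approximation is slightly optimistic but shows the same gap of 19 points.

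**The case against.** The study is observational and descriptive. Its primary objective is to describe post-embolization syndrome, adverse events and treatment-related mortality, and section 6.1 serves that with frequencies, percentages and confidence intervals. Finding risk factors is not among the stated objectives. The chi-square screen is exploratory and unpowered, and replacing it alters no primary estimate. **This stands**, and it limits the weight of the point. It does not remove it: section 6.1 itself commits to identifying related variables and to a 0.05 threshold, so the coding should be settled beforehand.

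The practical gain may be modest. At 10% events and OR 1.7 the continuous test has only about 42% power, and at the 1% rate nothing works. The simulations also assume a linear log-odds effect, which favours the continuous term by construction. **Both stand** and belong with the figures.

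Prespecified cut-points with a trend test would also cure the open choice of threshold. **True**, and this is an acceptable second choice, though it still loses information within groups.

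A reader might infer that the plan expects toxicity to rise with tumour size and then picks a test that blunts that very relation. The documents do not support this. Section 5.1 links the syndrome to necrotic volume, which follows from treatment and is not a listed variable. Tumour size would be the reader's proxy for it.

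**Conclusion.** The point holds in a limited form. Chi-square is the only *association* test for complications, though not their only analysis. As written, it forces grouping of age and tumour size at unspecified cut-points and ignores the ordering of Child-Pugh points and nodule count.

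The size of the loss is conditional. A reader might take about a third as the general figure, but that belongs to one case, a median split of a normal predictor. The plan fixes neither split nor distribution, and the plausible range runs from roughly 6% to over 50%. At OR 1.7 per SD with a normal predictor, a median split costs about 14 points of power at 10% events (42 − 28) and 19 points at 30% (76 − 57). Event rates, odds ratios and linearity are assumptions.

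Nor must all the graded variables be cut: Child-Pugh has three levels within eligibility and nodule count is a count, so what is lost there is ordering. The consequence is confined to the exploratory screen of the more frequent complications. The change is worth making because it is better and costs almost nothing, not because the primary results are at risk.

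**What to change.** In section 6.1, state that associations with complications will be examined by univariable logistic regression, as already planned for mortality, with a Firth penalty when events are few. Enter age and tumour size as continuous terms and Child-Pugh points and nodule count as ordered scores. Report odds ratios with 95% confidence intervals and label the analysis exploratory. Keep chi-square or exact tests for truly categorical variables such as gender, etiology, biliary prosthesis and shunt.

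If grouping is preferred for presentation, fix the cut-points before the data are examined and use a trend test.

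The text should not present tumour size as the predictor that the plan links to post-embolization syndrome.

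The cost is SAP wording only. The variables are already listed for collection, and both logistic regression and SAS 9.4 are already in the plan.
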